9.7 Rescue treatment

Initial treatment period and maintenance treatment period

If medically necessary (i.e., to control intolerable AD symptoms), rescue treatment for AD may be provided to trial subjects at the discretion of the investigator. For the purpose of efficacy analysis, subjects who receive rescue treatment during the initial treatment period will be considered as non-responders, but they will continue IMP treatment if rescue consisted of topical medications.

TCI may be used for rescue, but should be reserved for problem areas only, for example face, neck, intertriginous and genital areas, etc. If possible, investigators should attempt to limit the first step of rescue therapy to topical medications, and escalate to systemic medications only for subjects who do not respond adequately after at least 14 days of topical treatment.

If a subject receives rescue treatment with systemic corticosteroids or non-steroidal systemic immunosuppressive drugs (cyclosporine, methotrexate, mycophenolate mofetil, azathioprine, etc.), IMP will be immediately discontinued (see Section 9.8.2, reasons for temporary discontinuation of IMP). After the treatment with these medications is completed, IMP may be resumed if deemed appropriate by the investigator and sponsor's medical expert, but not sooner than 5 half-lives after the last dose of systemic rescue medication.

Investigators should make every attempt to conduct efficacy and safety assessments (for example disease severity scores, safety labs) immediately before administering any rescue treatment. An unscheduled visit may be used for this purpose, if necessary.

Trial ID: LP0162-1325	Date: 14-Aug-2018	Version: 4.0
		Page 60 of 169

Open-label tralokinumab arm only

From Week 16 through safety follow-up (FU1 [Week 66] or FU2 [Week 82]) subjects may use mild to moderate strength TCS and/or TCI as needed (prn usage) on lesional skin at the investigator's discretion (see Appendix 9 for TCS classification and examples). Use of TCS and TCI should be recorded as concomitant medication.

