# 6.3 Rescue medication

Rescue medication is defined by the following algorithm: Concomitant medications with Dermatitis atopic or Dermatitis infected as the preferred term for the indication and either ATC2 code H02 or D07, or ATC4 code D11AH or Preferred name Methotrexate, Ciclosporin, Azathioprine, Mycophenolate-mofetil, Mycophenolate-sodium, Mycophenolate-acid or Dupilumab.

According to the protocol investigators should make every attempt to conduct efficacy and safety assessments immediately before administering any rescue treatment. Therefore, if rescue medication has start date the same day as an efficacy assessment, then the assumption will be that the assessment is not influenced by the rescue medication, see also Section 6.8.4.

Rescue medication will be summarised separately for the initial and maintenance period. In addition, a summary table of rescue medication by type (topical and systemic) and by overall group (corticosteroids, immunosuppressants and other) will be made.

For subjects continuing with maintenance or open-label treatment at Week 16, the table of rescue medication during initial treatment period will include rescue medication taken (but not necessarily initiated) between the first dose of initial treatment and the first dose of either maintenance or open-label treatment. For subjects who do not continue with maintenance or open-label treatment, the table of rescue medication during initial treatment period will include medications taken after the first dose and before the (nominal) Week 16 visit (or before day 7\*16=112 after first dose, in case the (nominal) Week 16 visit did not take place).

The table of rescue medication during the maintenance treatment period will include rescue medication taken (but not necessarily initiated) after the first maintenance dose and exclude rescue medication initiated during the follow-up period.

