#### Trial periods

The time from exposure start to exposure end will be divided into initial period, maintenance period and open-label period, and remaining time after exposure end will be assigned to the follow-up period as shown in Table 4 (ADaM variable APHASE). The ADaM variable APERIODC will indicate the latest treatment (initial, maintenance or open-label) at any given time point, thus not including a follow-up period (Table 5).

Trial ID: LP0162-1325	Date: 20-May-2019	Version: 1.0
		Page 27 of 31

ADUASE	Start of pariod	End of noniad (only if star	t data a
Table 4: Start a	nd end time of trial	periods (ADaM variable APH	IASE).

APHASE	Start of period	End of period (only if start date exists)
Initial	Exposure start	Date and time (minus 1 second) of first maintenance
period		dose (if existing)
		else
		Date and time (minus 1 second) of first open-label dose
		(if existing)
		else
		Exposure end
Maintenance	Date and time of	Date and time (minus 1 second) of first open-label dose
period	first maintenance	(if existing)
	dose (if existing)	else
		Exposure end
Open-label	Date and time of	Exposure end
period	first open-label	
	dose (if existing)	
Follow-up	Exposure end	Date of safety follow-up visit (if existing) at time
period 	(plus 1 second)	23:59:00
		else
		Date of last contact at time 23:59:00

1) Only applicable if date of last contact is not equal to date of exposure end.

APERIODC	Start of period	End of period (only if start date exists)
Initial period	Exposure start	Date and time (minus 1 second) of first maintenance
		dose (if existing)
		else
		Date and time (minus 1 second) of first open-label dose
		(if existing)
		else
		Date of last contact at time 23:59:00
Maintenance	Date and time of	Date and time (minus 1 second) of first open-label dose
period	first maintenance	(if existing)
	dose (if existing)	else
		Date of last contact at time 23:59:00
Open-label	Date and time of	Date of last contact at time 23:59:00
period	first open-label	
	dose (if existing)	

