#### Concomitant medication

For the purpose of associating concomitant medication with trial periods, the convention will be that the start time of day of concomitant medications is 23:59:59, and end time is 00:00:00, unless the start day is equal to the end day in which case both start and end time will be assumed to be 23:59:59. As a consequence, rescue medication starting on the day of transfer between two periods will be associated with the latter period only, and rescue medication ending on the day of transfer between two periods will be associated with the start period only is equal to the end day).

Unlike adverse events which are assigned to a single period based on their start date only, a concomitant medication can be associated with more than one period.

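### Read literally, the SAP rule for the maintenance-period rescue table has no stop at the first open-label dose, which conflicts with the SAP's own period definitions

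*SAP*

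**What the plan says.** **Definition of rescue.** SAP 6.3 identifies rescue from the concomitant medication records: "Concomitant medications with Dermatitis atopic or Dermatitis infected as the preferred term for the indication and either ATC2 code H02 or D07", or certain other codes or named drugs. The definition carries no condition on treatment arm or trial period.

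**Tables.** SAP 6.3 states: "Rescue medication will be summarised separately for the initial and maintenance period". For subjects who continue at Week 16, the initial-period table covers rescue taken "between the first dose of initial treatment and the first dose of either maintenance or open-label treatment". The maintenance-period table "will include rescue medication taken (but not necessarily initiated) after the first maintenance dose and exclude rescue medication initiated during the follow-up period". The first rule has a start and a stop. The second has a start and a single exclusion.

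**Periods.** In SAP 6.8.2, Tables 4 and 5 both end the maintenance period of a transferred subject at "Date and time (minus 1 second) of first open-label dose". SAP 6.8.4 adds that "rescue medication starting on the day of transfer between two periods will be associated with the latter period only".

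**Topicals after transfer.** For the open-label arm, protocol 9.7 says that "subjects may use mild to moderate strength TCS and/or TCI as needed (prn usage) on lesional skin at the investigator's discretion", and asks for this use to be recorded as concomitant medication. Protocol 9.6 exempts open-label subjects from its prohibition of TCS, but lists TCI as prohibited without such an exemption.

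**The concern.** A subject who loses response in the maintenance period may transfer to open-label tralokinumab and then use a topical that the protocol allows there. The entry goes into the same records that the rescue algorithm searches. It falls after the first maintenance dose and before follow-up, so the words of 6.3 include it. The table would then mix rescue on blinded treatment with permitted treatment on open-label drug.

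The mixture need not be even across arms, because it depends on how many subjects transfer. A reader comparing regimens on their need for rescue could see a difference that partly reflects what happened after subjects had left those regimens.

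**Working it through.** **1. The texts side by side.**

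| Rule | Start | Stop at first open-label dose? | Follow-up |
|---|---|---|---|
| 6.3, initial table (subjects continuing at Week 16) | First initial dose | Yes (or first maintenance dose) | Not applicable |
| 6.3, maintenance table | First maintenance dose | Not stated | Rescue initiated there excluded |
| 6.8.2 Table 4, maintenance period | First maintenance dose | Yes | Outside the period, which otherwise ends at exposure end |
| 6.8.2 Table 5, maintenance period | First maintenance dose | Yes | Inside the period if no transfer, because it runs to last contact |

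Section 6.3 cites 6.8.4, but only for assessments on the day rescue starts. It does not cite 6.8.2, whereas section 6.5 explicitly adopts 6.8.2 for exposure.

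**2. Length of the literal window.** Transfer can occur from Week 22 (protocol 7.1). Follow-up begins after exposure end, which is Week 52 for a completer. Up to 52 − 22 = 30 weeks of open-label treatment can therefore fall inside the window.

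**3. The plan's own figures.** The rescue table has no stated figure. The only planning numbers that bear on transfer are in protocol 12.1, where power is given as above 99% for all four maintenance comparisons at the 4% level. The lowest is IGA, Q4W against placebo (50% of 70 against 5% of 35):
- Pooled rate = (35 + 1.75)/105 = 0.35.
- Null SE = √[0.35 × 0.65 × (1/35 + 1/70)] = 0.0987.
- Alternative SE = √(0.05 × 0.95/35 + 0.5 × 0.5/70) = 0.0702.
- Power = Φ[(0.45 − 2.054 × 0.0987)/0.0702] = Φ(3.52) = 99.98%.

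The other three exceed 99.99%, so the stated power reproduces.

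**4. Planned Week 52 non-response, as an upper proxy for transfer.** Non-responders = n × (1 − planned response).

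| | Q2W | Q4W | Placebo | Total |
|---|---|---|---|---|
| IGA | 70 × 0.20 = 14.0 | 70 × 0.50 = 35.0 | 35 × 0.95 = 33.25 | 82.25 |
| Share of total | 17% | 43% | 40% | |
| EASI75 | 94 × 0.10 = 9.4 | 94 × 0.45 = 42.3 | 47 × 0.95 = 44.65 | 96.35 |
| Share of total | 10% | 44% | 46% | |

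The proxy is an upper one because every transferred subject is a non-responder, while non-response also includes missing data, rescue, and loss of response short of the transfer criteria. The two responder groups overlap, so the rows must not be added.

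**5. Illustration under the literal rule.** Added percentage = t × u × (1 − planned response). Here t is the share of non-responders who transferred and u is the share of those who used a topical afterwards. Neither is in the documents. I assume t = 50–100% and u = 25–75%, equal across arms, so t × u runs from 0.125 to 0.75.

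| | Q2W | Q4W | Placebo |
|---|---|---|---|
| IGA, added points | 2.5–15 | 6–38 | 12–71 |
| IGA, added subjects | 2–11 | 4–26 | 4–25 |
| EASI75, added points | 1–8 | 6–34 | 12–71 |
| EASI75, added subjects | 1–7 | 5–32 | 6–33 |

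For any given t and u these are upper bounds. A transferred subject who already had rescue before transfer is counted anyway and adds nothing. With the stop in place and complete dates, topicals started after transfer add zero in every arm.

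**6. Reach.** Protocol 12.3.6.1 already makes transferred subjects non-responders at Week 52. Every transfer criterion in protocol 7.1 requires loss of EASI75 at three consecutive visits; for subjects with IGA 0 or 1 at Week 16 it also requires IGA of at least 2 or 3, respectively. Relapse as defined in protocol 12.3.6.2.1 has therefore occurred before transfer.

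**The case against.** The strongest reply is that the stop is already there. The table is described as covering the maintenance treatment period, 6.8.2 ends that period before the first open-label dose in both tables, and 6.8.4 says how medication is tied to periods. On this view the follow-up exclusion is also explained. Under Table 5 the maintenance period of a subject who never transfers runs to last contact, so follow-up has to be removed by hand, while open-label time does not.

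Much of this stands. It may well be what the authors meant, and it rules out saying that the table will certainly be wrong. It does not remove the conflict. Section 6.3 gives its own inclusion rule without adopting either table. Under Table 4 the follow-up exclusion would be redundant; under Table 5 it makes sense, but 6.3 does not say that Table 5 governs. Two programmers could follow the SAP and produce different tables.

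A reader might also infer that most of the subjects wrongly counted would be on placebo. The documents do not support that. With 2:2:1 allocation, placebo makes up 40–46% of planned non-responders, about as many as Q4W. Only the percentage within arm is clearly highest on placebo.

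Finally, the SAP does not decode its ATC codes, so that D07 and D11AH capture TCS and TCI is an assumption. For TCS it is a safe one, because protocol 12.3.6.1 counts TCS as rescue and the SAP plans a split into topical and systemic rescue.

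**Conclusion.** The point holds as a conflict inside the SAP, conditional on the literal reading of 6.3. The missing stop is plain on the page; whether the table would be miscounted depends on which section the programmer follows. If 6.3 is followed as written, permitted open-label topicals count as maintenance rescue. The inflation is then probably largest on placebo, then Q4W, then Q2W, as a percentage within arm. That ordering rests on the planned response rates and on equal transfer and topical-use shares across arms. The size cannot be determined from the documents, and the ranges shown are illustrative upper bounds.

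A reader might take this as a threat to the efficacy results. It is not: the table is descriptive, and no Week 52 responder analysis, relapse analysis, significance level or power figure changes. The correction is worth making because it is cheap and the table invites a comparison between arms.

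The disagreement between protocol 9.6 and 9.7 on TCI is separate and needs reconciling. The point stands on TCS alone.

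**What to change.** In SAP 6.3, state that the maintenance-period table includes rescue medication taken after the first maintenance dose and before the first open-label dose (if any), excluding medication initiated during follow-up. Refer to 6.8.2 and 6.8.4 for the period boundaries. A medication begun before transfer and continued afterwards would still count, which agrees with 6.8.4, where one medication may belong to more than one period.

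Tabulate topical treatment used after transfer separately, as concomitant treatment in the open-label period.

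The sponsor should reconcile protocol 9.6 and 9.7 on TCI in the open-label arm, so that the separate table is labelled consistently with the protocol.

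The cost in the SAP is one sentence, one date condition in the program and one extra descriptive table. No new data are needed.

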# 6.4 Compliance

Compliance will be summarised and listed.

# 6.5 Exposure

The exposure time during the initial, maintenance and open-label periods, respectively, will be defined as detailed in Section 6.8.2. Exposure time will be summarised and listed.

Patient years of exposure (PYE) for a period will be calculated as the difference between the start date and time and the end date and time for the period divided by 60x60x24x365.25.

# 6.6 Analysis of Efficacy

Efficacy will be analysed as described in the Clinical Trial Protocol.

[figure not shown]
# 6.6.1 Multiple testing procedure

To control the overall type 1 error rate, the primary analyses of the primary estimands for the primary and secondary endpoints for the initial and maintenance treatment will for the US submission follow a dedicated modified confirmatory testing hierarchy as outlined in Panel 1 below.

Trial ID: LP0162-1325	Date: 20-May-2019	Version: 1.0
		Page 13 of 31

#### Panel 1 Testing procedure for US submission

Arrows indicate order of testing when superiority is shown for all endpoints within a box. DLQI, Dermatology Life Quality Index; EASI75, at least 75% reduction in Eczema Area and Severity Index score; IGA, Investigator's Global Assessment; Q2W, every 2 weeks; Q4W, every 4 weeks.

IGA 0/1 at Week 16 between tralokinumab and placebo is evaluated at a 5% significance level. If the test is significant, EASI75 at Week 16 between tralokinumab and placebo is evaluated at a 5% significance level. If the second test is also significant, Pruritus at Week 16 between tralokinumab and placebo is evaluated at a 5% significance level.

If all three tests are significant, the significance level (alpha) will be split between the analyses of the 2 secondary endpoints at Week 16 and the analyses of the 2 maintenance endpoints at Week 52. These groups of tests are tested in parallel with alpha=1% for the endpoints at Week 16 and with alpha=4% for the maintenance endpoints at Week 52.

Trial ID: LP0162-1325	Date: 20-May-2019	Version: 1.0
		Page 14 of 31

The evaluations of the 2 secondary endpoints at Week 16 between tralokinumab and placebo will use the Holm method (3) for 2 ordered p-values at a 1% significance level to adjust for multiplicity.

The hypotheses for the maintenance treatment endpoints will be tested sequentially in the specified order at the 4% significance level. The next hypothesis will only be tested if the former was significant.

If all p-values for the 2 secondary endpoints at Week 16 are significant, then the hypotheses for the maintenance treatment endpoints can be evaluated at a 5% significance level. Conversely, if all p-values for the maintenance endpoints are significant, then the hypotheses for the 2 secondary endpoints at Week 16 can be evaluated at a 5% significance level.

For non-US submissions, the testing hierarchy defined in the protocol will be applied.

# 6.6.2 Primary and secondary binary endpoints

#### Sensitivity analysis 2 for the primary estimand (binary endpoints)

In the sensitivity Analysis 2 for the primary estimand, the protocol specifies that "If subjects have withdrawn due to an AE or due to lack of efficacy, they are still considered non-responders". Such subjects will be identified based on their reason for permanent discontinuation of IMP.

## Sensitivity analysis 3 for the primary estimand (binary endpoints)

A tipping point analysis using multiple imputation (MI) as an additional sensitivity analysis (not described in the protocol) for the primary estimand for the primary endpoints (IGA 0/1 and EASI75) and the secondary binary endpoint (reduction of Pruritus NRS weekly average of at least 4 (yes/no); Pruritus NRS  $\geq$  4) will be done.

The purpose of the sensitivity analysis is to assess the robustness of results of the primary analysis for the primary estimand with respect to the assumption regarding missing Week 16 data among subjects who did not use any rescue medication. The procedure will be as follows: subjects in the tralokinumab arm with missing Week 16 data will per default be considered non-responders while missing Week 16 data (i.e. response yes (=1)/ no (=0)) for subjects in the placebo arm who did not use rescue medication will be imputed from a Bernoulli distribution with parameter p (ranging from 0 to 1). By varying the parameter p, different percentages of placebo subjects will be assumed to be responders (deviating from the

Trial ID: LP0162-1325	Date: 20-May-2019	Version: 1.0
		Page 15 of 31

default zero (0) percent of the primary estimand). The tipping-point is then found as the value of p (in the range from 0 to 1) which changes the conclusion (of the primary analysis) from significant to non-significant.

Based on published data from other placebo-controlled clinical trials conducted in subjects with moderate-severe atopic dermatitis, the response rate for IGA 0/1, EASI75 and Pruritus NRS  $\geq$  4 at Week 16 among all placebo subjects is low (in the order of 10% for IGA 0/1 and Pruritus NRS  $\geq$  4, and 15% for EASI75, respectively). Thus, a tipping-point value (p) above 0.1 for IGA 0/1 and Pruritus NRS  $\geq$  4 and above 0.15 for EASI75, respectively, is not considered to be clinically plausible. As indicated above, p=0 corresponds to the primary analysis for the primary estimand. The MI procedure will include the following steps for each value of p:

• 100 copies of the dataset will be generated (seed=11109925) and missing Week 16 data will be imputed for subjects in the placebo arm from a Bernoulli distribution with parameter p.

For each of the 100 complete data sets, the difference in response rates will be analysed as specified for the primary analysis for the primary estimand and the estimates and standard errors from the 100 analyses will be combined using Rubin's rule to form a unique point estimate and standard error.

# 6.6.3 Continuous secondary endpoints

## Primary analysis of primary estimand (continuous secondary endpoints)

It is specified in the protocol that the continuous secondary endpoints will be analysed using a repeated measurements model on the post baseline responses up to Week 16. Data collected after permanent discontinuation of IMP or after initiation of rescue medication will not be included in the analysis.

However, some subjects may not have any post-baseline data collected before initiation of rescue medication. To ensure that all subjects are included in the analysis, the baseline value will for these subjects be carried forward as the first post-baseline assessment, corresponding to imputing a change of 0 at the first post-baseline assessment.

Tetriary (composite) estimand (continuous secondary endpoints)

For the continuous secondary endpoints (i.e. change in SCORAD and DLQI), an analysis is introduced where subjects who received rescue medication are considered non-responders. This new analysis aim to estimate the treatment effect for a 'Composite' estimand which is currently not pre-specified in the protocol for the continuous secondary endpoints. Thus, a new tertiary 'Composite' estimand for the continuous secondary endpoints is introduced.

Primary analysis for the tertiary (composite) estimand (continuous secondary endpoints): Data retrieved at Week 16 for subjects who have permanently discontinued IMP prior to Week 16 will be included in the analysis. Subjects who prior to the Week 16 visit have received rescue medication will be considered non-responders by using worst observation carried forward (including the baseline value).

Missing Week 16 data among subjects who did not use rescue medication will be imputed using MI (100 copies of the dataset, seed=11109925) assuming missing at random (MAR) within arms (based on sequential use of an ANCOVA model for Week 2, 4, 6, .. and 16). For subjects who dropout without any use of rescue medication, missing data at subsequent visits will be imputed under the assumption that the subject adheres to the randomised treatment regimen, i.e. the stepwise imputation model will be estimated based on available data from all subjects but excluding individual subject data captured after initiation of rescue medication or permanent discontinuation of IMP. For each of the 100 imputed datasets, the continuous secondary endpoint will be analysed using an ANCOVA model with effects of treatment, region, baseline disease severity (IGA 3 or 4), and baseline value. The estimates and standard errors from the 100 analyses will be combined using Rubin's rule to form a unique point estimate and standard error.

As a sensitivity analysis for the tertiary estimand, a tipping point analysis using MI will be performed with the purpose to assess the robustness of results of the primary analysis for the tertiary estimand with respect to the MAR assumption regarding missing Week 16 data among subjects who did not use any rescue medication. The tipping analysis will assess how severe the departure from the MAR assumption in the tralokinumab arm has to be in order to impact the results (i.e. changes the conclusion of primary analysis of the tertiary estimand) from significant to non-significant).

The tipping point analysis will be performed using the MAR imputed Week 16 data from primary analysis of the tertiary estimand. For each of the 100 imputed datasets,  $\Delta$  will be added to the imputed values for subjects in the tralokinumab arm ( $\Delta = 0$  implies MAR) and thereby the imputed values will be 'shifted' by  $\Delta$ . Each of the 100 modified imputed datasets

Trial ID: LP0162-1325	Date: 20-May-2019	Version: 1.0
		Page 17 of 31

will then be analysed in the same way as for the primary analysis for the tertiary estimand. The tipping-point is then found as the value of  $\Delta$  which changes the conclusion (of the primary analysis) from significant to non-significant and will be judged from a clinical point of view.

The implications of the missing not at random assumptions will be compared to the implication of the missing at random assumptions by visual inspection.

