12.3.5.2.1 Primary estimand for the continuous secondary endpoints: 'hypothetical'

The primary estimand for the continuous secondary endpoints will be:

• Treatment difference in change from baseline to Week 16 in SCORAD and DLQI, respectively, if all subjects adhered to the treatment regimen in the sense that they did not discontinue IMP permanently and no rescue medication was made available before Week 16.

The primary estimand assesses the expected benefit when adhering to the treatment regimen tralokinumab with no rescue medication as compared to a treatment regimen with placebo with no rescue medication.

Primary analysis of the primary estimand (continuous secondary endpoints)

Data collected after permanent discontinuation of IMP or after initiation of rescue medication will not be included in the analysis.

The endpoints will be analysed using a repeated measurements model on the post baseline responses up to Week 16 with an unstructured covariance matrix, Kenward-Roger approximation to estimate denominator degrees of freedom, and the mean modelled as follows (shown for change from baseline in SCORAD):

Change from baseline in SCORAD

= treatment \times visit + baseline SCORAD \times visit + region + baseline IGA

This model assumes that data is missing at random within each treatment arm. The estimates will be presented with nominal p-values and 95% CI at each visit. The primary comparison between tralokinumab and placebo will be at Week 16.

Sensitivity analysis for the primary estimand (continuous secondary endpoints)

Rather than assuming that observations are missing at random within each treatment arm it is assumed that missing data from subjects who discontinue treatment/receive rescue medication in the tralokinumab arm will resemble data from subjects from the placebo arm who do not discontinue treatment/receive rescue medication. Imputation of missing data at Week 16 will be done using a pattern mixture model where missing data in the tralokinumab arm as well as the placebo arm will be imputed from the placebo arm (using a so-called copy-reference approach). The procedure for the change from baseline in SCORAD at Week 16 is described below. The same procedure will be applied for the DLQI endpoint.

1. Intermittent missing values will be imputed in each group using a Markov Chain Monte Carlo method to obtain a monotone missing data pattern and 100 copies of the dataset will be generated (seed=29099725).

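### SAP 6.6.3 enters an invented zero change as an observed first visit for subjects rescued before any post-baseline value, at odds with the hypothetical estimand and missing-at-random model for SCORAD and DLQI

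*SAP*

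**What the plan says.** Protocol 12.3.5.2.1 defines the primary estimand for the two continuous secondary endpoints as the treatment difference if all subjects "did not discontinue IMP permanently and no rescue medication was made available before Week 16". It follows that "Data collected after permanent discontinuation of IMP or after initiation of rescue medication will not be included in the analysis". The remaining data go into a repeated-measures model "with an unstructured covariance matrix", and the protocol states the assumption: "This model assumes that data is missing at random within each treatment arm".

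SAP 6.6.3 observes that "some subjects may not have any post-baseline data collected before initiation of rescue medication". Its remedy is that "the baseline value will for these subjects be carried forward as the first post-baseline assessment, corresponding to imputing a change of 0". The reason given is: "To ensure that all subjects are included in the analysis". Only the first post-baseline assessment is filled in. Later visits, including Week 16, stay missing and are handled by the model.

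Three neighbouring provisions matter:

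- The protocol's copy-reference sensitivity analysis for the same estimand imputes missing Week 2 values from a regression model, not with a zero.
- SAP 6.6.3 also introduces a separate tertiary composite estimand in which rescue counts as failure.
- Neither document plans the primary analysis without the zero, or a count of the subjects affected.

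**The concern.** The estimand asks what would have happened had rescue not been available. For a subject rescued before the first assessment, the protocol model answers from comparable subjects in the same arm. The SAP instead supplies a fixed answer, no change from baseline, and treats it as assessed. That is a failure-type single imputation inside an analysis that is not meant to treat rescue as failure, when the SAP already has a composite estimand for that purpose.

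Because the covariance is unstructured, the Week 2 value informs the Week 16 estimate, so the zero does not stay at Week 2. These are confirmatory tests: the Week 16 secondary endpoints are tested by Holm at 1%, rising to 5% if all maintenance tests succeed. The primary estimate would then rest partly on a constant that the stated assumption does not justify.

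**Working it through.** **Plan's own figure.** There is none on this point. The sample-size section covers only binary endpoints; its power above 99% for 585 versus 195 subjects reproduces (30% versus 10% and 40% versus 15% both give power above 0.999), but it says nothing about SCORAD or DLQI. The documents give no early-rescue rate, Week 2 change or between-visit correlation. Apart from the arm sizes, every input below is an assumption, and the figures are for SCORAD only.

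**Formula.** Let f be the share of an arm rescued before any post-baseline value, m the mean Week 2 improvement in that arm, and b the slope of the Week 16 value on the Week 2 value. Replacing the missing-at-random prediction by zero moves the arm's Week 2 mean towards no change by f × m, and its Week 16 mean by b × f × m. With T for tralokinumab and P for placebo:

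shift in the Week 16 difference (T minus P) = b × (fT × mT − fP × mP)

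A negative shift favours tralokinumab. This requires fP/fT > mT/mP.

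**Closed-form results.**

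| Early rescue T / P | Week 2 improvement T / P | b | Calculation | Shift (points) |
|---|---|---|---|---|
| 2% / 5% | 9 / 6 | 0.7 | 0.7 × (0.18 − 0.30) | −0.08 |
| 4% / 10% | 9 / 6 | 0.9 | 0.9 × (0.36 − 0.60) | −0.22 |
| 2% / 3% | 9 / 6 | any | b × (0.18 − 0.18) | 0 |
| 4% / 3% | 9 / 6 | 0.5 to 0.9 | b × (0.36 − 0.18) | +0.09 to +0.16 |
| 4% / 10% | 8 / 6 | 1.0 | 1.0 × (0.32 − 0.60) | −0.28 |
| 5% / 5% | 12 / 4 | 1.0 | 1.0 × (0.60 − 0.20) | +0.40 |

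The last two rows are the extremes of the combinations examined within b 0.4 to 1.0, improvements of 8 to 12 (tralokinumab) and 4 to 6 (placebo), and early rescue of 1–5% and 2–10%. The outer corners of those ranges go a little further: 1.0 × (0.01 × 8 − 0.10 × 6) = −0.52, and 1.0 × (0.05 × 12 − 0.02 × 4) = +0.52.

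The break-even ratio fP/fT is 8/6 = 1.33, 9/6 = 1.5, 10/6 = 1.67 or 12/4 = 3.0, depending on the Week 2 improvements.

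**Simulation check.** 1,500 trials per scenario, 585 versus 195 subjects, eight visits, Week 2 means −10 and −6, Week 16 means −28 and −16, b = 0.60, maximum likelihood by sequential regression. With early rescue unrelated to outcome:

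| Early rescue T / P | Closed form | Simulated, zero minus missing at random |
|---|---|---|
| 1% / 2% | −0.012 | −0.013 |
| 2% / 5% | −0.060 | −0.061 |
| 4% / 10% | −0.120 | −0.135 |
| 5% / 5% | +0.120 | +0.111 |

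The empirical SD of the estimate is 1.64 to 1.72, so the largest shift here is 0.135/1.70 = 0.08 SD.

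**If early-rescued subjects would have done worse without rescue.** Where placebo has more of them (the first three rate pairs), the missing-at-random analysis departs from the full-data answer by +0.08 to +0.71, against tralokinumab. The zero rule leaves +0.07 to +0.47. The largest gap between the two is −0.236 (4% / 10%), or 0.236/1.77 = 0.13 SD. At equal rates of 5%, the zero makes matters worse: about +0.13 against about +0.02.

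**The case against.** The strongest defence has four parts.

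1. **Few subjects can be affected.** The first scheduled visit is Week 2. Protocol 9.7 asks for assessments immediately before rescue, at an unscheduled visit if necessary. SAP 6.3 counts a same-day assessment as uninfluenced by rescue, and SAP 6.8.6 lets unscheduled data from Days 8 to 21 stand in for a missing Week 2 visit. This stands, and it limits the size.
2. **Only one visit is set.** Week 16 is not set to failure, and a reader who infers that it is would be wrong. The model still estimates Week 16, but conditional on a value nobody observed.
3. **Missing at random may itself be wrong.** Someone rescued within two weeks may well have fared worse. Where placebo has more early rescue, the simulation shows the zero removing part of that bias. This also stands. But it is a missing-not-at-random argument, which the SAP does not make, and it belongs in a labelled sensitivity analysis.
4. **Other analyses exist.** Copy-reference, treatment-policy and composite analyses with a tipping point are planned for these endpoints. None isolates the effect of the zero.

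A reader might also infer that the rule tends to favour tralokinumab, because placebo subjects are more likely to need early rescue. The documents do not support that. Each zero costs the tralokinumab arm more when its expected Week 2 improvement is larger, so an excess of placebo rescue is not enough; the ratio must pass the break-even. Neither document supplies the quantities needed to decide this.

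**Conclusion.** The mismatch is real and follows from the two texts alone: a constant is entered as data in a model whose estimand excludes rescue and whose stated assumption is missing at random within arm. Inclusion of every subject does not justify it. The rule misses that goal anyway, since a subject who stops IMP without rescue before any post-baseline value is not covered. Nor does a subject with only a baseline value need an invented visit for the protocol model to be valid under its own assumption.

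The consequence is probably small: a fraction of a SCORAD point under every assumption tried, below a tenth of the estimate's SD in the simulations where early rescue is unrelated to outcome, and up to 0.13 SD where it is related. The sign is open. No change to a confirmatory conclusion is shown, and no size was worked out for DLQI. This is a minor correction, worth making because it aligns the analysis with its estimand.

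**What to change.** In SAP 6.6.3, remove the zero from the primary analysis. Leave these values missing. If every subject must appear in the model, impute the first visit under missing at random within arm from baseline value, region and baseline IGA, using multiple imputation so that the uncertainty is carried. State that the same handling applies to subjects who stop IMP before any post-baseline value.

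Keep the zero-change version as a sensitivity analysis labelled missing not at random, and report the number of affected subjects per arm for SCORAD and DLQI separately. Including baseline in the response vector with a common mean is an alternative, but it replaces the protocol's model and is optional.

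The cost is SAP wording and one extra analysis; no new data are needed. The drawback is that the missing-at-random version may be biased if early-rescued subjects would have done worse, which the zero-change sensitivity analysis would help to show.
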